Rather than an alternative medium for implementation of existing interventions designed for in-person contact, social media may be a true 'game changer'^{74,76,77,121,122} to engage hard to reach individuals. While many online behavioral interventions exist, including some that use social media,¹⁶⁹ ours will be the first to use social media to facilitate uptake of a biomedical intervention. E-PrEP will connect the target population (YMCSM) to a new prevention tool (PrEP) through rapid linkage to medical care, accelerating diffusion of PrEP. Given the paucity of data regarding social media-based interventions to change health-related behavior, E-PrEP may have a marked impact on future bio-behavioral interventions, especially those that include diffusion of innovation.

Social media offers the power of scale and efficiency for large potential impact, even with relatively low intensity interventions.^{77,109,122} Similarly, PrEP, if widely adopted in high-risk populations and offered with behavioral interventions, could markedly decrease HIV infection rates. Social media-based, peer-led approaches like E-PrEP could be used to enhance efforts by community based and other organizations that employ internet-assisted or peer-outreach strategies to improve health.⁷⁶

Aims: To test the feasibility and preliminary efficacy of E-PrEP for increasing PrEP adoption in a cluster-randomized controlled trial.

Methods

Participants: The 16-20 peers will be randomized 1:1 to either E-PrEP or BxNow (control condition). They will then recruit n=240 total participants (120 for E-PrEP and 120 to BxNow). Each Peer will recruit approximately n=15 participants.

Inclusion criteria: Male or trans individuals; Ages 18-29; Have had unprotected anal sex with a male partner in the prior 12 months; Fluent in English or Spanish; Are HIV negative or unknown status (self-report); Identify as Black and/or Latino

Exclusion criteria: YMCSM or trans individuals who do not consent/assent to study; Are currently taking PrEP for HIV prevention, not currently using at least one of 3 social media sites that will be used for the E-PrEP intervention (e.g. not using Facebook, Twitter, Tumblr).

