Benefits: Although there are no direct potential benefits to participants, possible benefits include increase access to healthcare education and new HIV prevention information. Additionally, E-PrEP has the potential to increase reach of HIV prevention programs and services, and reduce HIV risk behaviors in YMCSM, but will require pilot testing and refinement. If effective, E-PrEP could be broadly implemented by health centers and community-based organizations, and reduce HIV transmission and promote healthy behaviors. Given the steps that we will take to minimize the chances of breach of confidentiality, participating in this study presents low risk and the risk/benefit ratio is favorable. For more information about the risk and benefits please consult the Protection of Human Subjects document section I.6 attached below.

Procedures

PROCEDURES FOR PEER LEADER Participation:

Peer Leaders (Peers) Recruitment: In addition to the study participants, we will recruit 16-20 New York city based YMCSM Peer Leaders 18-29 to partner with us on this project. The initial pool of Peers will be from our recently completed *theSEXword* pilot and additional Peers as needed will be recruited through the Adolescent AIDS Program YMSM outreach program or Bronx based community organizations involved in my Bronx Pride Initiative partnership (see Facilities section) and on the Montefiore-Einstein Center for AIDS Research Community Advisory Board, which I help facilitate. Recruited Peers will have all completed participation in a face-to-face HIV prevention and leadership facilitation intervention (the 'Popular Opinion Leader' program¹⁵² or a similar program offered at the Adolescent AIDS Program and at other community agencies), identified by agency staff as an individual who appears to be a "leader" in their specific YMCSM community, has large online social networks (i.e. >300 YMCSM 'friends'). Our current *theSEXword* YMCSM Peers were recruited within 1 week and we had to create a wait-list of individuals wanting to participate. On average, our current Peers have approximately 500 unique MSM of color "friends" on their social networks and it is not unusual for many of them to have >1,000 "friends" or "followers" on their social media profiles. Therefore we do not anticipate having any difficulty recruiting Peer Leaders that meet our criteria and are appropriate for this project.

Study Procedures for Peer Leaders (Peers)

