We will use community based participatory research principles for implementing the study with Peers. Peer Leaders will meet up to 9 times during the course of the study (over a 7-10 week period) for ongoing trainings in online outreach, implementation of the online outreach, and providing ongoing feedback. Meetings will take place in a private conference room at Montefiore Medical Center. Peers may additionally meet for two follow-up visits after completion of the study to provide additional feedback in focus group discussions. The 9 study visits/sessions will be spread out over a course of 7-10 weeks.

To evaluate the impact of our trainings and the effects of the study on the Peers, we will use a mixed methods evaluation design. First, all Peers will complete a written informed consent at the first session (Visit 1) before we collect any information, conducted by a study coordinator or the PI. Next, the Peers will complete a very brief survey on basic socio-demographics, experience with using social media, and general information about their existing online social networks (e.g. number of Facebook Friends or Instagram Followers). At each subsequent visit, we will collect process data on the online outreach intervention by asking the Peer Leader participants in a group setting to discuss 1) any challenges or issues that have come up over the past week(s), 2) suggestions for improvement of online outreach, 3) and to report on any technical or other issues that they may have encountered with conducting online outreach.

After completion of the study visits with the Peer Leaders, we will elicit feedback on their experiences participating in the study using an informal discussion guide in a focus group setting. The data/information will be captured by a study coordinator who will take written notes during all of the sessions. No names or identifying information will be collected or attached to the process data collected. We will conduct up to 2 such sessions, once relatively soon after completion of the initial phase of the study (After week 6 of the intervention as described in the 'General Participants' section below and then after week 12 of data collection) to fully inform and guide online outreach practices and to capture any potentially relevant issues that may have come up during the follow-up period for the general participants.

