Compensation for Peer Leader participants. Peers will be compensated for their time and travel and incentivized to actively participate in each visit by providing a ClinCard up to a total of \$425 over the course of the study for 9 visits. Peer Leaders will receive the incentive by having it added to a debit card, after attending each visit. The payments will occur as follows: Visit 1: \$30, Visit 2: \$40, Visits 3-4: \$45 each, Visits 5-7: \$50 each, Visit 8: \$55, Visit 9: \$60. Peers will not receive any compensation for visits in which they do not attend. Additionally, Peer Leaders may be able to receive an additional \$60 for each of two optional follow-up visits after the completion of intervention (up to two more visits).

Training in Ethical Conduct of Research for Peer Leaders: Although we will be collecting data from the Peers in order to evaluate the study and the Peers are also research subjects in this study, as part of the overall intervention, Peers will be conducting online recruitment and outreach and therefore we will make sure that Peers have a clear understanding of their roles in this capacity. We will initially conduct a two-session training with the Peers where they will go through our community research ethics training. I adapted this training from a World Health Organization training manual for lay community members, such as our Peers, participating as 'community researchers' to make accessible to them training in research ethics. It covers topics in history of research ethics, privacy and confidentiality, vulnerable subjects, ethical recruitment practices, protecting against risks, minimizing risks, and personal safety and conduct. This training has previously used with community partners for whom the CITI course is inaccessible due to literacy and/or language barriers. Additionally, we will have ongoing trainings throughout the project period in online privacy, security issues, and confidentiality with information. Peers in the study are not key personal, however we believe it is important that they do understand research ethics.

PROCEDURES FOR GENERAL PARTICIPANTS

Recruitment:

1. We will first randomize the 16 to 20 peers, 1:1 to either E-PrEP or BxNow (control condition).
2. Peers will then recruit n=240 participants total from their personal online social networks to their assigned condition (E-PrEP or BxNow). On average, each peer will recruit approximately 15 participants each.

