I.1 HUMAN SUBJECTS INVOLVEMENT AND CHARACTERISTICS: In table 1 below, we summarize the project’s activities, the number of participants who we project will participate in each activity, and the amount of reimbursement each participant will receive for these activities.

Table 1. Summary of project activities and compensation		
Activities	Participants	Compensation per participant
To pilot test E-PrEP and determine preliminary efficacy		
120 online surveys in control group at each time point (0, 6, 12 weeks)	120 YMCSM participants	(online gift-cards or via a Clincard) \$20/\$30/\$40/ \$20 assessment
120 online surveys in experimental group at each time point (0, 6, 12 weeks)	120 YMCSM Participants	\$20/ \$30 / \$40 / \$20 assessment
Total	240 unique individuals	---

I.1.2. Participants: The 16 peers will be randomized 1:1 to either E-PrEP or BxNow (control condition). They will then recruit n=240 total participants (120 for E-PrEP and 120 to BxNow). Each Peer will recruit approximately n=15 participants. In an effort to support recruitment efforts, members of the research team will buy Facebook ads to outreach to potential participants. We will assign participants randomly with equal number to each of the peer members who are having trouble with recruitment.

Inclusion criteria: Male; Ages 18-29; Have had unprotected anal sex with a male partner in the prior 12 months; Fluent in English or Spanish; Are HIV negative or unknown status (self-report); Identify as Black and/or Latino

Exclusion criteria: YMCSM who do not consent/assent to study; Are currently taking PrEP for HIV prevention, not currently using at least one of 3 social media sites that will be used for the E-PrEP intervention (e.g. not using Facebook, Twitter, Tumblr).

Recruitment:

1. We will first randomize the 16 peers, 1:1 to either E-PrEP or BxNow (control condition).
2. Peers will then recruit n=240 participants total from their personal online social networks to their assigned condition (E-PrEP or BxNow). On average, each peer will recruit approximately 15 participants each.
3. Peers will actively recruit online within their pre-existing social networks using text messages, brief videos, and picture graphics, using whichever mode is deemed appropriate. These recruitment advertisements will be co-developed by the Peers and investigators. Peers will then post the designated messages to their online social networks.

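### Only 16-20 Peers are randomised and no restriction on the allocation is described, although network size and pilot status can be known beforehand; constrained allocation is a cheap improvement

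*Combined protocol and SAP*

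**What the plan says.** Methods (Participants) states: "The 16-20 peers will be randomized 1:1". Step 1 of Recruitment under Procedures for General Participants repeats this and places it before any participant is recruited. Section I.1.2 gives 16 Peers. The target is "120 for E-PrEP and 120 to BxNow", and "Each Peer will recruit approximately n=15 participants". No section names an allocation method, and none mentions stratification, matching, blocking, minimisation or constrained randomisation.

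Two Peer traits can be known before allocation:

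- **Network size.** Peer Leaders (Peers) Recruitment requires more than 300 friends in the target population. It reports an average of about 500 for current Peers, with many above 1,000. Study Procedures for Peer Leaders adds a Visit 1 survey covering "general information about their existing online social networks". Whether Visit 1 comes before randomisation is not stated.
- **Source.** The initial pool comes from the completed pilot, and "additional Peers as needed will be recruited through the Adolescent AIDS Program YMSM outreach program" or through Bronx community organisations. The pilot/new split is not given.

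The Analytic Plan handles imbalance in the analysis only. Groups are compared at baseline, relevant differences become covariates, and Peer is a random effect. A sensitivity analysis uses the participants' own network size and their perceived affinity to the Peer. The referring Peer appears as a subgroup variable, but that identifies the cluster and does not describe a trait of the Peer.

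**The concern.** With 8 to 10 units per arm, an unrestricted draw can easily give one arm the better-connected or more experienced Peers. The plan's own reasoning makes these traits relevant. Section I.5, item 9, says that a diffusion intervention works through the tie between a person and their network, and Peers word their own posts, so experience may affect delivery.

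The safeguards do not clearly reach this. A random effect carries between-Peer variance into the standard error but does not correct a realised imbalance. Participant-level covariates only partly stand in for a Peer trait, and with 16-20 clusters few Peer-level terms can be added after the fact. The Power Analysis section gives the primary purpose as feasibility and an effect-size estimate for a later application. One lopsided draw could shift that estimate.

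**Working it through.** **The plan's own figure.** For 20% v 5%, two-sided 0.05 and 80% power, the two-proportion formula gives 75.1 per arm before rounding. The continuity correction raises this to 88 per arm, or 176 in total, and 176/0.8 = 220. The stated 220 is reproduced. It treats participants as independent, so it says nothing about Peer-level balance. The plan states no probability of imbalance, so that is derived here.

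**Chance imbalance on one continuous Peer trait.** With k Peers per arm, the arm difference in SD units has standard error sqrt(2/k), and P(|d| > c) = 2 × [1 − Φ(c / sqrt(2/k))].

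| Peers | SE | P(>0.25 SD) | P(>0.5 SD) | P(>0.8 SD) |
|---|---|---|---|---|
| 8 v 8 | 0.50 | 62% | 32% | 11% |
| 10 v 10 | 0.45 | 58% | 26% | 7% |

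**Pilot status (hypergeometric).** If half the Peers are from the pilot (assumed), a 6:2 split or worse has probability 13% with 16 Peers, and 7:3 or worse has 18% with 20. If a quarter or three quarters are from the pilot, a difference of 4 or more Peers has probability 3-8%.

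**Either trait.** Simulation used right-skewed network sizes above 300 with mean about 500, and half pilot Peers. The chance of more than 0.5 SD on log network size, or a difference of 4 or more pilot Peers, was 43% with 16 Peers and 42% with 20.

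**What constraining achieves.** There are C(16,8) = 12,870 equal allocations of 16 Peers. All were enumerated for 200 simulated sets of Peers, and the best 10% (1,287) kept each time.

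- Constraining one continuous trait only: maximum difference about 0.07 SD.
- Constraining network size and pilot status together (8 of 16 from the pilot, assumed): maximum about 0.18 SD on network size, with pilot status exactly balanced. This is the figure that applies to the fix below.

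**What adjustment does to power.** Assumptions: 240 × 0.8 / 16 = 12 analysed per Peer, 96 per arm; ICC not given in the documents. Design effect = 1 + 11 × ICC × (1 − share of between-Peer variance explained). SE = sqrt[(0.16 + 0.0475) × design effect / 96]. Power is from the noncentral t with 14 df unadjusted, and 12 df after two Peer-level terms.

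| ICC 0.05, 16 Peers | Design effect | SE | 0.15/SE | df | Power |
|---|---|---|---|---|---|
| Unadjusted | 1.55 | 0.0579 | 2.59 | 14 | 67% |
| Adjusted, 0% explained | 1.55 | 0.0579 | 2.59 | 12 | 66% |
| Adjusted, 10% explained | 1.495 | 0.0568 | 2.64 | 12 | 68% |
| Adjusted, 30% explained | 1.385 | 0.0547 | 2.74 | 12 | 71% |

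At ICC 0.01, even 30% explained leaves power at about 81%, with or without adjustment.

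**The case against.** The strongest case against is that the mechanism is weak under this design. Each Peer recruits about 15 people whatever the network size. Content goes to private groups with standardised media, topics and sequence, and Peers who struggle to recruit are given participants from Facebook ads. Friend count therefore sets neither cluster size nor dose. All Peers must also have completed a leadership programme, so only pilot participation varies. This stands in part: the documents give no evidence on how strongly either trait predicts intention. The advertising route could also work the other way, by giving an arm of smaller-network Peers more participants who do not know their Peer, but that too is inference.

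Four stronger readings are tempting, and the documents do not support them:

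- A reader might infer simple, coin-flip allocation. The method is not stated, and 120 per arm at about 15 per Peer points to equal numbers of Peers.
- A reader might infer that large imbalance is likely. On any one trait, a difference above 0.5 SD is less likely than not, and one above 0.8 SD has a chance of 7-11%.
- A reader might infer that the trial is biased. Randomisation keeps the estimate unbiased in expectation; the loss is in precision and credibility.
- A reader might credit a power gain to constrained allocation. The change calculated above comes from covariate adjustment alone, and it can be slightly negative.

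**Conclusion.** The point holds as a modest, low-cost design improvement. Few units are randomised, two plausible predictors can be known beforehand, no restriction is described, and no Peer-level trait is named in the analysis. The risk of a difference above 0.5 SD on one trait is about 26-32%, given equal arms and a normal approximation. The benefit to the effect estimate depends on how far the traits predict intention, which is unknown. The likely change in power from adjustment runs from about 1 point lost to about 4 points gained at ICC 0.05 with 16 Peers, and is close to nothing at ICC 0.01. The stated sample size does not change.

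**What to change.** - State the allocation method, and reconcile the number of Peers (16-20 in the main protocol, 16 in Sections I.1.2 and I.1.3).
- Obtain network size and pilot/new status for all Peers before allocation, for example by placing randomisation after the Visit 1 survey.
- Allocate 1:1 by covariate-constrained randomisation on both traits, drawing at random from, say, the best 10% of allocations. Stratification is an alternative, but coarse cells do less. In the simulation above, a split at median network size within pilot status lowered the chance of more than 0.5 SD from 34% to 14% with 16 Peers. With 20 Peers, where cells hold 5, it fell only from 29% to 26%.
- Pre-specify both traits as Peer-level covariates in the primary model, so that the analysis reflects the allocation and does not depend on observed differences.

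Cost: a short allocation script, a randomisation date that waits for the Peer data, and 2 degrees of freedom. No extra participants are needed.
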